#### **5.5. Criteria for Temporarily Delaying Enrollment/Randomization/Administration of Study Intervention of a Participant**

Not applicable.

## 6. Study Intervention(s) and Concomitant Therapy

Study intervention is defined as any investigational intervention(s), marketed product(s), placebo, or medical device(s) intended to be administered to/used by a study participant according to the study protocol.

### 6.1. Study Interventions Administered

Intervention Name	Tirzepatide (LY3298176)	Placebo
Type	Drug	Drug
Dose Formulation	Single-dose pen	Single-dose pen
Dosage Level(s)	10 mg QW, 15 mg QW	Not applicable
Route of Administration	SC	SC
Use	Experimental	Placebo
IMP and NIMP	IMP	IMP
Sourcing	Provided centrally by the sponsor and dispensed via IWRS	
Packaging and Labeling	Study intervention will be provided in autoinjectors (single-dose pens), packaged in cartons to be dispensed. Clinical study materials will be labeled according to country regulatory requirements	

Abbreviations: IMP = investigational medicinal product; IWRS = interactive web-response system; NIMP = non-investigational medicinal product; QW = once-weekly; SC = subcutaneous.

There are no restrictions on the time of day each weekly dose of study intervention is given, but it is advisable to administer the SC injections on the same day and same time each week. The actual date, time, and injection details of all dose administrations will be recorded in the diary by the participant. If a dose of study intervention is missed, the participant should take it as soon as possible unless it is within 72 hours of the next dose, in which case that dose should be skipped, and the next dose should be taken at the appropriate time. The day of weekly administration can be changed if necessary, as long as the last dose was administered 72 or more hours before.

All participants will inject study intervention subcutaneously in the abdomen or thigh using the injection supplies provided; a caregiver may administer the injection in the participant's upper arm. A new autoinjector will be used for each injection. If study intervention is to always be injected in the same body region, participants should be advised to alternate injection sites each week.

### 6.1.1. Medical Devices

The combination products provided for use in the study are tirzepatide autoinjector (or matching placebo). Any medical-device incidents, including those resulting from malfunctions of the device, must be detected, documented, and reported by the investigator throughout the study (see Section 10.3).

## 6.2. Preparation, Handling, Storage, and Accountability

- The investigator or designee must confirm appropriate storage conditions have been maintained during transit for all study intervention received and any discrepancies are reported and resolved before use of the study intervention.
- Only participants enrolled in the study may receive study intervention. Only authorized study personnel may supply study intervention. All study intervention must be stored in a secure, environmentally controlled, and monitored (manual or automated) area in accordance with the labeled storage conditions with access limited to the investigator and authorized study personnel.
- The investigator or authorized study personnel are responsible for study intervention accountability, reconciliation, and record maintenance (that is, receipt, reconciliation, and final disposition records).
- Further guidance and information for the final disposition of unused study interventions are in the provided instructions.

## 6.3. Measures to Minimize Bias: Randomization and Blinding

All participants will be centrally randomly assigned to study intervention using an IWRS. Before the study is initiated, the log in information and directions for the IWRS will be provided to each site.

Study intervention will be dispensed at the study visits summarized in SoA.

Returned study intervention should not be re-dispensed to the participants.

This is a double-blind study in which participants and study personnel, are blinded to study intervention. The IWRS will be programmed with blind-breaking instructions. In case of an emergency, the investigator has the sole responsibility for determining if unblinding of a participants' intervention assignment is warranted. Participant safety must always be the first consideration in making such a determination. If the investigator decides that unblinding is warranted, the investigator should make every effort to contact the sponsor prior to unblinding a participant's intervention assignment unless this could delay emergency treatment for the participant. If a participant's intervention assignment is unblinded, the sponsor must be notified immediately within 24 hours of this occurrence. The date and reason that the blind was broken must be recorded.

If an investigator, site personnel performing assessments, or participant is unblinded, the participant must be discontinued from the study. In cases where there are ethical reasons to have the participant remain in the study, the investigator must obtain specific approval from a sponsor clinical research physician (CRP) for the participant to continue in the study.

## Stratification

Participants will be stratified at randomization per ISA by country/geographic region, baseline AHI (moderate/severe), and gender.

### 6.4. Study Intervention Compliance

A record of the number of single-dose pens dispensed to and taken by each participant must be maintained and reconciled with study intervention and compliance records. Intervention start and stop dates, including dates for intervention delays and/or dose reductions will also be recorded.

Treatment compliance for each visit interval is defined as taking at least 75% of the required doses of study intervention. Similarly, a participant will be considered significantly noncompliant if he or she is judged by the investigator to have intentionally or repeatedly taken more than the prescribed amount of medication (more than 125%).

Participants considered to be poorly compliant with their medication and/or the study procedures will receive additional training and instruction, as required, and will be reminded of the importance of complying with the protocol.

### 6.5. Dose Modification

Dose modification is permitted for management of intolerable GI symptoms during the first 24 weeks of the treatment period (Section 6.5.1).

Participants who do not tolerate at least 10 mg even after the described measures, including 1 de-escalation and re-escalation attempt, will be discontinued from the study intervention but remain in the study for continued follow-up.

Interventions to optimize study intervention tolerance and adherence may be employed throughout the study and include, but are not limited to, brief temporary interruptions (Section 7.1.2) and use of additional medications to manage GI symptoms (for example, nausea, vomiting, and diarrhea).

#### 6.5.1. Management of Participants with Gastrointestinal Symptoms

In participants who experience intolerable GI symptoms (for example, nausea, vomiting, or diarrhea) at any time during the study, the following measures are recommended:

- counselling on dietary behaviors that may help mitigate nausea and vomiting, (for example, eating smaller meals, splitting 3 daily meals into 4 or more smaller ones, and stopping eating when they feel full).
- if symptoms persist despite #1, prescribing symptomatic medication (for example, antiemetic or antidiarrheal medication), at the investigator's discretion.
- if symptoms persist despite #1 and #2, interrupting study intervention for 1 dose, provided the participant has taken the last 3 weekly doses. Study treatment should be resumed at the assigned dose immediately, either alone or in combination with symptomatic medication, which can also be utilized to manage symptoms (Section 6.8).

During the first 24 weeks of the treatment period (20-week dose escalation plus 4 weeks), participants unable to tolerate 2.5 mg or 5 mg (despite the interventions mentioned above) will be discontinued from the study intervention but remain in the study.

For participants unable to tolerate any dose between 7.5 mg and 15 mg inclusive, despite the above measures, the investigator should contact Lilly to consider a dose de-escalation step with subsequent re-escalation by 2.5 mg every 4 weeks in a blinded fashion, to reach either the 10-mg or 15-mg dose as described below.

Only 1 cycle of dose de-escalation and re-escalation is permitted during the first 24 weeks of the treatment period. MTD is either 10 mg or 15 mg. Dose modifications after the first 24 weeks of the treatment period are not permitted. For temporary study treatment discontinuation, see Section 7.1.2.

Participants who tolerate

- 10 mg, but do not tolerate 12.5 mg or 15 mg even following the above measures, including 1 de-escalation and re-escalation attempt, will continue on 10 mg as their MTD dose.
- 12.5 mg, but do not tolerate 15 mg even after the above measures, including 1 de-escalation and re-escalation attempt, will continue on 10 mg as their MTD dose.
- 15 mg will continue on 15 mg as their MTD dose.

## 6.6. Continued Access to Study Intervention after the End of the Study

Tirzepatide will not be made available to participants after conclusion of the study.

## 6.7. Treatment of Overdose

Study intervention overdose (more than the specified number of injections in less than 72 hours) will be reported as an AE.

In the event of an overdose, the treating physician should:

- Contact the medical monitor immediately.
- Evaluate the participant to determine, in consultation with the medical monitor, whether study intervention should be interrupted or whether the dose should be reduced.
- Closely monitor the participant for any AE/SAE and laboratory abnormalities until study intervention no longer has a clinical effect.

## 6.8. Concomitant Therapy

Participants will be permitted to use concomitant medications that they require during the study, except certain medications (Section 6.8.2) that may interfere with the assessment of efficacy and safety characteristics of the study treatments.

Investigative-site staff will inform participants that they must consult with the investigator or a designated site staff member upon being prescribed any new medications during the study. This may not be possible when initiated for treatment of medical emergencies, in which case, the participant will inform the investigator or a designated site staff member as soon as possible.

Nonstudy medications taken by participants who are screened but not randomly assigned to study intervention will not be reported to Lilly unless an SAE or AE occurs that the investigator believes may have been caused by a study procedure.

Any medication or vaccine (including over-the-counter or prescription medicines, vitamins, and/or herbal supplements, or other specific categories of interest) that the participant is receiving at the time of screening or receives during the study must be recorded along with:

- Reason for use
- Dates of administration including start and end dates

The medical monitor should be contacted if there are any questions regarding concomitant or prior therapy.

### **6.8.1. Management of Incident Diabetes**

Incident diabetes is defined when any 1 of the following occur after randomization (American Diabetes Association 2020):

- unequivocal hyperglycemia (random glucose  $\geq 200$  mg/dL) with signs or symptoms of hyperglycemia
- within a 4-week period, any 2 of the following criteria are observed or 1 abnormal value is observed and confirmed:
  - HbA1c  $\geq 6.5\%$  (48 mmol/mol)
  - FG or 0-hour serum glucose from 2-hour OGTT  $\geq 126$  mg/dL (7.0 mmol/L)
  - 2-hour glucose  $\geq 200$  mg/dL (11.1 mmol/L) by a 2-hour OGTT
  - initiation of any medication for the treatment of diabetes

Participants who develop type 2 diabetes during the study will be

- provided with and trained to use a glucometer
- educated on the signs and symptoms of hypoglycemia and its treatment (see Section 10.3.7.1), and
- provided a diary to record hypoglycemic episodes per Section 10.3.7.1.

Participants will be referred to their usual care provider and provided with a letter showing the study results indicative of diabetes. The decision to further evaluate, to initiate antihyperglycemic therapy, and the choice of antihyperglycemic medication will be at the discretion of the participant's usual care provider, with the exception of use of DPP-4 inhibitors and open-label GLP-1R agonists, which are prohibited in the study (Section 6.8.2). Monitoring for hypoglycemia includes capture of events as defined in Section 10.3 (Appendix 3). Date of diabetes diagnosis will be captured in the AE CRF.

Initiation of metformin for the treatment of diabetes is permitted, but metformin should not be initiated during the study for the treatment of other metabolic conditions (for example, polycystic ovary syndrome and diabetes prevention).

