### 6.8.2. Prohibited Concomitant Medications

The following medications are prohibited during the study:

- DPP-4 inhibitors
- Open-label GLP-1R agonists
- Stimulants (for example, modafinil, armodafinil, solriamfetol, pitolisant, amphetamine, dextroamphetamine, dextmethylphenidate, methylphenidate, and lisdexamfetamine)
- medications that may cause significant weight gain (such as, but not limited to, paroxetine, tricyclic antidepressants, atypical antipsychotic and mood stabilizers).
- Medications that may cause weight loss (such as, but not limited to, liraglutide, semaglutide, orlistat, sibutramine, phenylpropanolamine, mazindol, phentermine, lorcaserin, naltrexone/bupropion, phentermine/topiramate combination, pramlintide, zonisamide, and topiramate)
- OTC, herbal, or supplemental medications that, in the opinion of the investigator, may interfere with the study
- hypnotics, mirtazapine, opioids, trazodone, pramlintide, sibutramine, orlistat, and zonisamide
- Systemic glucocorticoid therapy, per discussion with sponsor
- Use of any over-the-counter or prescription medications that could affect the evaluation of excessive sleepiness, per investigator discretion (such as, but not limited to, CBD oil, THC, etc.)
- Any glucose-lowering medication, including metformin

In addition,

- Active device treatment of OSA other than PAP therapy (for example, dental appliance), or other treatment that, in the opinion of the investigator, may interfere with study outcomes.

Participants who initiate and will not or cannot discontinue a prohibited medication, device, or other treatment will be permanently discontinued from study intervention per Section 7.1.

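### Protocol 6.8.2 prohibits all glucose-lowering medication without exception, contradicting 6.8.1, which permits metformin and, two drug classes apart, other antihyperglycemics for incident diabetes

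*Protocol*

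**What the plan says.** - **Protocol 6.8 (Concomitant Therapy).** Participants may take the medications they need, "except certain medications (Section 6.8.2) that may interfere with the assessment of efficacy and safety characteristics of the study treatments". Section 6.8.2 is the only place named for what is not allowed.
- **Protocol 6.8.1 (Management of Incident Diabetes).** One of the listed criteria for incident diabetes is "initiation of any medication for the treatment of diabetes". Whether to start antihyperglycemic therapy, and which, is for the usual care provider, "with the exception of use of DPP-4 inhibitors and open-label GLP-1R agonists, which are prohibited in the study (Section 6.8.2"). The section then states: "Initiation of metformin for the treatment of diabetes is permitted". It rules out metformin for other metabolic conditions, such as polycystic ovary syndrome or diabetes prevention.
- **Protocol 6.8.2 (Prohibited Concomitant Medications).** DPP-4 inhibitors and open-label GLP-1R agonists each have their own bullet. The last drug bullet reads "Any glucose-lowering medication, including metformin". It carries no exception and no reference to 6.8.1. Participants who start a prohibited treatment and will not or cannot stop it "will be permanently discontinued from study intervention per Section 7.1".
- **Protocol 7.1.** Starting a prohibited medication, with a pointer to 6.8.2, is among the possible reasons for permanent discontinuation of study intervention.
- **SAP Table GPIF.3.2.** The efficacy analysis set (EAS) drops data after study intervention stops (last dose + 7 days). The full analysis set (FAS) keeps data whether or not the participant adheres.

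**The concern.** The two sections give opposite instructions for the same participant: one who develops type 2 diabetes on study and is prescribed metformin or another antihyperglycemic outside the two named classes. Under 6.8.1 the participant takes it and stays on study drug. Under 6.8.2 the participant must stop it or come off study drug permanently.

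Two things are at stake. The first is care: a literal reading sets treatment for a new diagnosis against continued study drug, although 6.8.1 was written to avoid that choice. The second is consistent handling: sites could act differently on identical cases, and where study drug is stopped, the participant's later AHI values leave the efficacy-estimand analysis.

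**Working it through.** No sample size, power or alpha figure bears on this point, so the check is a comparison of the current texts.

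**1. The sections side by side, for a participant with incident type 2 diabetes**

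| Question | 6.8.1 | 6.8.2 |
|---|---|---|
| Metformin to treat the diabetes | Permitted expressly | Prohibited by name |
| DPP-4 inhibitor or open-label GLP-1R agonist | Prohibited | Prohibited |
| Any other antihyperglycemic | Usual care provider's choice | Prohibited by the last drug bullet |
| Study drug if such treatment continues | No stop called for | Permanent discontinuation |

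The sections agree only on the second row.

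**2. Does any text give one section precedence?** None in the master protocol or SAP. The pointers run towards 6.8.2: 6.8 refers there for what is not allowed, 6.8.1 cites it for the two excluded classes, and 7.1 cites it for stopping study drug. The change table for Amendment c describes the addition of the blanket bullet as a clarification and does not list 6.8.1 as changed. That suggests how the conflict arose, but the conflict itself lies in current text.

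**3. Which rule was intended?**
- Under the literal 6.8.2 bullet, the express metformin permission and the two-class exception in 6.8.1 would have no meaning, and the separate DPP-4 and GLP-1R bullets in 6.8.2 would be redundant.
- Starting a diabetes medication is itself one of the incident-diabetes criteria in 6.8.1.
- Protocol 7.1 lists a diagnosis of T1DM, but not T2DM, as a reason to stop study drug.
- Protocol 9.3.5.2 allows for hypoglycemia analyses that exclude data after another antihyperglycemic is introduced.
- SAP 4.1.6 plans a summary of antihyperglycemic use in participants who develop type 2 diabetes.

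The last two items are not conclusive alone, since participants who stop study drug stay in the study and could be treated then. Taken together, the evidence points to 6.8.1.

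**4. What the literal reading does to the data.** The EAS cutoff is last dose + 7 days. Any PSG after it, out of the two planned post-baseline PSGs (Weeks 20 and 52), contributes no AHI value to the efficacy-estimand MMRM in SAP 4.3.1. Observed values after the stop remain in the FAS.

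**5. How many participants?** Protocol 5.2 excludes T1DM, T2DM and HbA1c of 6.5% or more at Visit 1. Neither document gives an expected rate of incident diabetes. The count cannot be derived.

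**The case against.** The strongest reply is that this is a missing cross-reference between adjacent sections and that the specific rule governs. Section 6.8.1 names metformin and separates treating diabetes from other uses; the note to exclusion 44 draws the same line at polycystic ovary syndrome and diabetes prevention. The change table calls the added bullet a clarification, which does not suggest an intent to reverse 6.8.1. Section 6.8 tells participants to consult the site about new prescriptions and sends questions on concomitant therapy to the medical monitor. Harm requires a site to apply 6.8.2 over 6.8.1, not ask, and have a participant who will not or cannot stop the drug. The ISAs, read together with the master protocol, might also settle the matter.

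Most of this stands as evidence of intent and limits the weight of the point. It does not remove the contradiction: no available text gives 6.8.1 priority, and asking the medical monitor helps only a site that notices the conflict.

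A reader might go further and infer that metformin is also caught by the open-ended bullet beginning "Medications that may cause weight loss (such as, but not limited to, liraglutide, semaglutide", because exclusion 44 lists glucose-lowering medication among weight-loss remedies. The documents do not support that. Exclusion 44 governs use before Visit 1, the weight-loss bullet does not name metformin, and 6.8.1 permits it expressly for diabetes.

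**Conclusion.** The contradiction is real in the master protocol and SAP, and 6.8.2 is wrong as written. The intended rule is evidently 6.8.1. Applied literally, 6.8.2 costs a newly diabetic participant either permitted treatment or study drug, and in the latter case ends that participant's EAS data at last dose + 7 days.

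The number affected is unknown. It is probably small, given that diabetes at entry is excluded, but that is a judgement and not a figure from the documents.

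A reader might infer a biased efficacy-estimand result, or try to count the AHI values lost. Neither follows. The loss per participant depends on when study drug stops relative to the PSGs, as it does for any early stop, and the documents do not give the delay from diagnosis to stopping. Nor does the EAS exclusion reach the treatment regimen estimand, which SAP 1.1.1 names as primary for the FDA application. A forced stop could change AHI values observed later and kept in the FAS, but nothing in the documents allows that to be sized.

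The conclusion assumes that neither ISA, which were not available, resolves the conflict.

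**What to change.** Keep the last drug bullet of Protocol 6.8.2, "Any glucose-lowering medication, including metformin", and add after it: *except as permitted for the treatment of incident diabetes in Section 6.8.1 (DPP-4 inhibitors and open-label GLP-1R agonists remain prohibited).* The term open-label must stay, because tirzepatide is itself a GIP/GLP-1R agonist and an unqualified ban would cover the study drug.

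The cost is the wording of one bullet, by amendment or clarification letter, with no new visits, procedures or analyses. Under Protocol 10.1.1 an amendment goes through IRB/IEC approval, so it is sensible to include the change in one already planned.

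If dosing has ended, rewording changes nothing for participants. The sponsor should then document, for each incident-diabetes case, which rule was applied and whether study drug was stopped because of it.

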### 6.8.2. Prohibited Concomitant Medications

The following medications are prohibited during the study:

- DPP-4 inhibitors
- Open-label GLP-1R agonists
- Stimulants (for example, modafinil, armodafinil, solriamfetol, pitolisant, amphetamine, dextroamphetamine, dextmethylphenidate, methylphenidate, and lisdexamfetamine)
- medications that may cause significant weight gain (such as, but not limited to, paroxetine, tricyclic antidepressants, atypical antipsychotic and mood stabilizers).
- Medications that may cause weight loss (such as, but not limited to, liraglutide, semaglutide, orlistat, sibutramine, phenylpropanolamine, mazindol, phentermine, lorcaserin, naltrexone/bupropion, phentermine/topiramate combination, pramlintide, zonisamide, and topiramate)
- OTC, herbal, or supplemental medications that, in the opinion of the investigator, may interfere with the study
- hypnotics, mirtazapine, opioids, trazodone, pramlintide, sibutramine, orlistat, and zonisamide
- Systemic glucocorticoid therapy, per discussion with sponsor
- Use of any over-the-counter or prescription medications that could affect the evaluation of excessive sleepiness, per investigator discretion (such as, but not limited to, CBD oil, THC, etc.)
- Any glucose-lowering medication, including metformin

In addition,

- Active device treatment of OSA other than PAP therapy (for example, dental appliance), or other treatment that, in the opinion of the investigator, may interfere with study outcomes.

Participants who initiate and will not or cannot discontinue a prohibited medication, device, or other treatment will be permanently discontinued from study intervention per Section 7.1.

